A Double-blind, Placebo-controlled, Crossover Study of Magnesium Supplementation in Patients with XMEN Syndrome

NIAID Protocol Number: 15-I-0161

Sponsored by: NIAID

Version Number: 9.0

Date: March 8, 2019

Principal Investigator: [name]

Study Staff Roster

Principal Investigator:

[name] Laboratory of Immunology (LI)/NIAID

Associate Investigators:

[name] LI/NIAID

[name] Laboratory of Host Defenses/NIAID

[name] LI/NIAID

[name], ScM, CGC LI/NIAID

[name] National Heart Lung and Blood Institute/
Cardiovascular and Pulmonary Branch

[name] Biostatistics Research Branch/NIAID

Study Coordinator:

[name] LCID/NIAID

Medical Advisory Investigator:

[name] LID/NIAID

Protocol Summary

Full Title:	A double-blind, placebo-controlled, crossover study of magnesium supplementation in patients with XMEN syndrome
Short Title:	XMEN syndrome and magnesium
Clinical Phase:	Phase 1 and 2
Conducted by:	NIAID/LI
Principal Investigator:	[name]
Sample Size:	n=20 (n=10 for each cohort)
Accrual Ceiling:	n=30
Study Population:	Patients \geq 6 years with X-linked immunodeficiency with magnesium defect and increased susceptibility to Epstein-Barr virus (EBV) infection and neoplasia (XMEN) syndrome. Subjects will be divided into 2 cohorts: Cohort 1 (high EBV): Subjects with baseline blood EBV viral load \geq 5,000 copies/mL or EBV log \geq 3.7 IU/mL. Cohort 2 (low/no EBV): Subjects with baseline blood EBV viral load <5,000 copies/mL or EBV log <3.7 IU/mL.
Accrual Period:	4 years
Study Design:	A randomized, double-blind, placebo-controlled, crossover study to evaluate the safety and efficacy of oral magnesium L-threonate in subjects with XMEN syndrome. In Part I, patients within each cohort will be randomized into 2 arms. Each arm will receive 12 weeks of either oral magnesium L-threonate or placebo followed by crossover treatment for another 12 weeks. Patients in cohort 1 who experience \geq 0.5-log reduction in the number of EBV-infected B cells and patients in cohort 2 who experience \geq 2-fold increase in NKG2D receptor expression on CD8 T cells during oral magnesium treatment as compared to placebo will have completed the study. Patients who do not meet these respective criteria will undergo a 2-week washout and transition to Part II in which they will be hospitalized to receive 3 days of IV MgSO ₄ . These patients will then restart escalating doses of oral magnesium and continue for 24 weeks, at which point participation will be complete.
Study Duration:	Start Date: 6/1/2015; End Date: 6/1/2020 Total length of individual subject participation: either 27 or 53 weeks

Study Agent/

Intervention Description: Part I: 12 weeks of oral magnesium L-threonate at escalating, weight-based doses ranging from 96 mg to 384 mg daily, and 12 weeks of placebo.

Part II: 3 days of IV MgSO₄ at 30 mg/kg/day, followed by escalating doses of oral magnesium L-threonate for 24 weeks.

Primary Objectives:

- Cohort 1: To investigate the efficacy of magnesium supplementation in patients with XMEN syndrome by comparing the absolute number of EBV-infected B cells after 12 weeks of oral magnesium and after 12 weeks of placebo.
- Cohort 2: To investigate the efficacy of magnesium supplementation in patients with XMEN syndrome by comparing NKG2D receptor expression on CD8 T cells after 12 weeks of oral magnesium and after 12 weeks of placebo.

Secondary Objectives:

- To assess the safety and tolerability of MgSO₄ IV infusion and oral magnesium L-threonate.
- To evaluate the effects of magnesium supplementation on intracellular free magnesium (Mg²⁺) concentrations in peripheral blood T cell lymphocytes.
- Contingent upon patient participation in Part II, to study the effect of 12 weeks vs. 24 weeks of oral magnesium supplementation after 3 days of IV magnesium on EBV viral load and number (or percent) of EBV-infected B cells (cohort 1) or NKG2D receptor expression on CD8 T cells (cohort 2) in patients with XMEN syndrome.
- To evaluate the difference in NKG2D expression between patients with high EBV titers and patients with low or negative titers.

Exploratory Objectives:

- To assess the effect of magnesium supplementation on lymphocyte subset measures.
- To quantify absolute and relative numbers of EBV-infected B cells using an assay combining cell-surface markers via flow cytometry and fluorescent *in situ* hybridization (FISH) analysis of the EBV genome.
- To study the effects of magnesium supplementation on preexisting abnormal biological markers, i.e., NKG2D expression in natural killer (NK) cells, anemia, neutropenia, thrombocytopenia, and abnormal liver enzymes.
- Assess the effect magnesium on clinical findings and health-related outcomes.

Primary Endpoints:

- Cohort 1: Difference between the absolute number of EBV-infected B cells (by EBV FISH) after 12 weeks of oral magnesium supplementation and after 12 weeks of placebo.
- Cohort 2: Difference between NKG2D expression in CD8 T cells after 12 weeks of oral magnesium supplementation and after 12 weeks of placebo.

Secondary Endpoints:

- Incidence and severity of adverse events (AEs) throughout the study.
- Contingent upon patient participation in Part II, differences in EBV viral load and number (or percent) of EBV-infected B cells (cohort 1) or NKG2D expression in CD8 T cells (cohort 2) by duration (12 weeks of IV+oral versus 24 weeks of IV+oral) of magnesium supplementation regimen.
- Change in the intracellular pool of free Mg²⁺ by duration of magnesium supplementation regimen.
- evaluate the difference in NKG2D expression between patients with high EBV titers and patients with low or negative titers.

Exploratory Endpoints:

- Change in CD4 T cell counts, B cell counts (or percent), and/or in NKG2D expression on NK (CD3-CD56+) cells.
- Quantification of EBV-infected B cells as determined by flow cytometry and FISH.
- Percent of anemia, neutropenia, thrombocytopenia, and abnormal liver enzymes.
- Difference in number and severity of infections between placebo and magnesium treatment periods.
- Difference in number of health-related days of missed school/work between placebo and magnesium treatment periods.
- Difference in number of emergency room visits and hospital admissions between placebo and magnesium treatment periods.

TABLE OF CONTENTS

Study Staff Roster.....	2
Protocol Summary	3
List of Abbreviations.....	8
Précis.....	10
1 Background Information and Scientific Rationale	11
1.1 Background and Summary of Relevant Pre-clinical Studies.....	11
1.1.1 Rationale	14
2 Study Objectives	16
2.1 Primary Objectives.....	16
2.2 Secondary Objectives	16
2.3 Exploratory Objectives	16
3 Study Design.....	16
3.1 Description of the Study Design	16
3.2 Study Endpoints.....	18
Primary Endpoints	18
Secondary Endpoints	18
Exploratory Endpoints	18
4 Study Population.....	18
4.1 Recruitment Plan	18
4.2 Subject Inclusion Criteria	18
4.3 Subject Exclusion Criteria	19
4.4 Justification for Exclusion of Children <6 years old	19
5 Study Agent/Interventions	19
5.1 Disposition and Dispensation.....	19
5.2 Formulation, Packaging and Labeling	19
5.3 Study Agent Storage and Stability.....	20
5.4 Preparation, Administration, and Dosage of Study Agent/Intervention(s)	20
5.4.1 Description.....	20
5.4.2 Dosing and Administration	20
5.5 Study Product Accountability Procedures	23
5.6 Concomitant Medications and Procedures	23
5.7 Drug Interactions	23

	Appendix C: Patient Medication Log	48
	Appendix D: Compensation Table.....	49

List of Abbreviations

AE	Adverse Event/Adverse Experience
CBC	Complete Blood Count with Differential
CMV	Cytomegalovirus
CNS	Central Nervous System
CRIMSON	Clinical Research Information Management System of the NIAID
CRP	C-Reactive Protein
CT	Computed Tomography
DNA	Deoxyribonucleic Acid
EBV	Epstein-Barr Virus
EKG	Electrocardiogram
ESR	Erythrocyte Sedimentation Rate
FDA	Food and Drug Administration
FISH	Fluorescent In Situ Hybridization
GCP	Good Clinical Practice
HHV8	Human Herpesvirus 8
HIV	Human Immunodeficiency Virus
HSV	Herpes Simplex Virus
ICH	International Conference on Harmonization
IDMRS	Investigational Drug Management Research Section
IRB	Institutional Review Board
IU	Inconvenience Unit
IV	Intravenous
LI	Laboratory of Immunology
LID	Laboratory of Infectious Diseases
MAGT1	Magnesium Transporter 1
MFI	Mean fluorescent intensity
Mg ²⁺	Magnesium Ion
MgSO ₄	Magnesium Sulfate
NCI	National Cancer Institute
NIAID	National Institute of Allergy and Infectious Diseases
NIH	National Institutes of Health
NK	Natural Killer (cells)
NKG2D	Natural Kill Cell Group 2-D Receptor
OCRPRO	Office of Clinical Research Policy and Regulatory Operations
OHRP	Office for Human Research Protections
PBMCs	Peripheral Blood Mononuclear Cells
PCR	Polymerase Chain Reaction
PT	Prothrombin Time
PTT	Partial Thromboplastin Times
RNA	Ribonucleic Acid
SAE	Serious Adverse Event/Serious Adverse Experience
SMC	Serum Magnesium Concentration
TCR	T Cell Receptor
UP	Unanticipated Problem

XMEN X-linked immunodeficiency with Magnesium deficiency, Epstein-Barr Virus infection and Neoplasia

Précis

[figure not shown]
X-linked immunodeficiency magnesium defect, Epstein-Barr virus (EBV) infection and neoplasia (XMEN) syndrome is a primary immunodeficiency caused by the loss of expression of the magnesium transporter 1 (MAGT1). This syndrome is associated with CD4 lymphopenia, chronic EBV infection in most patients, and EBV-related lymphoproliferative disorders. The loss of MAGT1 leads to impaired T cell activation and decreased expression of the activator receptor, NKG2D on natural killer (NK) cells and CD8 T cells, leading to decreased EBV-specific cytolytic function of these cells. Results of previous studies suggest that magnesium supplementation may be a viable therapeutic option for patients with XMEN.

The proposed study has 2 parts, and patients will be divided into 2 cohorts. Patients in cohort 1 (high EBV group) will have baseline blood EBV viral load \geq 5,000 copies/mL or EBV log \geq 3.7 IU/mL. Patients in cohort 2 (low/no EBV group) will have baseline blood EBV viral load $<$ 5,000 copies/mL or EBV log $<$ 3.7 IU/mL. Part I is a randomized, double-blind, placebo-controlled, crossover study to evaluate the safety and efficacy of oral magnesium L-threonate in patients with XMEN syndrome. Within each cohort, patients will be randomized to receive escalating doses of either placebo or oral magnesium L-threonate for 12 weeks. Patients will then receive the crossover treatment (magnesium or placebo) for an additional 12 weeks. For patients who experience a 0.5-log decrease in the number of EBV-infected B cells (cohort 1) or a \geq 2-fold increase in NKG2D receptor expression on CD8 T cells (cohort 2) with oral magnesium as compared to placebo, the study will be complete. Patients who do not meet this efficacy outcome will undergo a 2-week washout period and proceed to Part II, an open-label, non-randomized evaluation of intravenous magnesium sulfate ($MgSO_4$) followed by oral magnesium L-threonate. These patients will be hospitalized to receive 3 days of intravenous $MgSO_4$ in 3 daily doses totaling 30 mg/kg/day. They will then restart escalating doses of oral magnesium L-threonate and continue for the remaining 24 weeks of Part II. If conducted, Part II will allow for secondary analyses to compare different durations of magnesium supplementation.

1 Background Information and Scientific Rationale

1.1 Background and Summary of Relevant Pre-clinical Studies

Mg²⁺ is essential for many physiological processes. The majority of the intracellular Mg²⁺ (14 to 20 mM) is bound to nucleotides and proteins and is essential for energy metabolism, DNA transcription and protein synthesis [1]. The remaining unbound, intracellular free Mg²⁺ (0.5-1 mM) is tightly regulated. Under normal conditions, the magnesium transporter, MAGT1, participates in the intracellular Mg²⁺ homeostasis and facilitates a transient Mg²⁺ influx into T cells, which is a necessary step in the activation of those cells [2]. The loss of MAGT1 expression causes an immunodeficiency named XMEN syndrome associated with CD4 lymphopenia, chronic EBV infection, and EBV-related lymphoproliferative disorders [2-4]. XMEN patients may present with an inverted CD4:CD8 ratio and a reduced number of CD31+ cells in their naïve CD4 T cell population, suggesting decreased thymic output [2, 3]. Additionally XMEN is associated with B cell lymphocytosis due to chronic EBV infection [3]. The loss of MAGT1 leads to impaired T cell activation and decreased expression of the activator receptor, NKG2D on NK cells and CD8 T cells, leading to decreased EBV-specific cytolytic function of these cells [2-4]. These individuals may have reduced immunoglobulin production or a defective specific antibody response secondary to T lymphocyte dysfunction, but B cells are generally unaffected [2-4]. In addition to EBV infection, some XMEN patients have recently been found to have increased susceptibility to disease associated with other viral infections, including human herpesvirus 8 (HHV8) and herpes simplex virus (HSV). Similarly, non-EBV driven malignancies (eg, sarcoma) have been reported. **Figure 1** summarizes the main clinical and molecular features of XMEN disease.

Inositol 1,4,5-Triphosphate (IP₃) and its receptor. (C) Model of role of MAGT1 in Mg²⁺ expression. In XMEN patients, the absence of MAGT1 leads to the chronic reduction of intracellular free Mg²⁺, which is required to maintain the expression of NKG2D. Adapted from [3]

We analyzed null mutations in the X-linked gene encoding for MAGT1 in a group of 8 subjects. These mutations lead to the loss of MAGT1 protein expression. At a cellular level, the loss of MAGT1 has 2 main consequences: i) the loss of a TCR-induced transient Mg^{2+} influx required for optimal T cell activation and ii) a chronic decrease in intracellular free Mg^{2+} without affecting the total or bound intracellular Mg^{2+} . This latter defect is linked to the loss of expression of the NKG2D receptor on NK and CD8 T cells. *In vitro* studies of XMEN patients' cells show that supplementation of the tissue culture medium with 1 mM, 2 mM, or 5 mM of $MgSO_4$ leads to a partial but significant recovery of NKG2D expression and better cytotoxic function in both NK and CD8 T cells. Preliminary observational *in vivo* studies in 4 patients with XMEN have shown oral magnesium L-threonate to be a safe and well-tolerated therapeutic option. These patients experienced improvement in intracellular magnesium concentrations, NK and CD8 T cell function, and NKG2D expression, decreased EBV viral loads and a decrease in the number of EBV-infected B cells as determined by FISH (Figure 2). Furthermore, in our experience, EBV-naïve patients who have started magnesium supplementation have also reported less frequent infections.

[figure not shown]
[figure not shown]

Figure 2. Effect of Mg²⁺ supplementation with Mg²⁺ L-threonate in 4 XMEN patients

baseline SMC. Furthermore, magnesium administered at the dose proposed in our protocol has safely been given to treat a variety of conditions in both children and adults.

2 Study Objectives

2.1 Primary Objectives

- Cohort 1: To investigate the efficacy of magnesium supplementation in patients with XMEN syndrome by comparing the absolute number of EBV-infected B cells after 12 weeks of oral magnesium and after 12 weeks of placebo.
- Cohort 2: To investigate the efficacy of magnesium supplementation in patients with XMEN syndrome by comparing NKG2D receptor expression on CD8 T cells after 12 weeks of oral magnesium and after 12 weeks of placebo.

2.2 Secondary Objectives

- To assess the safety and tolerability of MgSO₄ IV infusion and oral magnesium L-threonate.
- To evaluate the effects of magnesium supplementation on intracellular free Mg²⁺ concentrations in peripheral blood T cell lymphocytes.
- Contingent upon patient participation in Part II, to study the effect of 12 weeks vs. 24 weeks of oral magnesium supplementation after 3 days of IV magnesium on EBV viral load and number (or percent) of EBV-infected B cells (cohort 1) or NKG2D receptor expression on CD8 T cells (cohort 2) in patients with XMEN syndrome.
- To evaluate the difference in NKG2D expression between patients with high EBV titers and patients with low or negative titers.

2.3 Exploratory Objectives

- To assess the effect of magnesium supplementation on lymphocyte subset measures.
- To quantify absolute and relative numbers of EBV-infected B cells using an assay combining cell-surface markers via flow cytometry and FISH analysis of the EBV genome.
- To study the effects of magnesium supplementation on preexisting abnormal biological markers, i.e., NKG2D expression in NK cells, anemia, neutropenia, thrombocytopenia, and abnormal liver enzymes.
- Assess the effect magnesium on clinical findings and health-related outcomes.

3 Study Design

[figure not shown]
3.1 Description of the Study Design

Patients enrolled onto the study will be divided into 2 cohorts. Patients in cohort 1 (high EBV group) will have baseline blood EBV viral load \geq 5,000 copies/mL or EBV log \geq 3.7 IU/mL. Patients in cohort 2 (low/no EBV group) will have baseline blood EBV viral load $<$ 5,000

copies/mL or EBV log <3.7 IU/mL. The study will be conducted in 2 parts; for each patient, participation in Part II is contingent upon the outcome of Part I. Part I is a randomized, double-blind, placebo-controlled, crossover study to evaluate the efficacy of oral magnesium L-threonate compared to placebo. Following an initial washout of magnesium-containing supplements, patients within each cohort will be randomized into 2 arms (**Figure 5**). Arm 1 will receive 12 weeks of magnesium supplementation followed by 12 weeks of placebo. Arm 2 will receive 12 weeks of placebo followed by 12 weeks of magnesium supplementation. Magnesium supplementation will consist of escalating doses of daily, orally self-administered magnesium L-threonate.

After 24 weeks of study, patients who show a 0.5-log (3.16-fold or 68.35%) reduction in the number of EBV-infected B cells (cohort 1) or or a ≥ 2 -fold increase in NKG2D receptor expression on CD8 T cells (cohort 2) during oral magnesium treatment as compared to placebo will end study participation. Such patients may remain on oral magnesium after completion of the study under the supervision of a primary care physician. Patients in whom oral magnesium was not clearly effective will begin a 2-week washout and proceed to Part II. Such patients will be hospitalized to receive 3 days of IV MgSO₄ administered 3 times per day for a total daily dose of 30/mg/kg/day. Then they will restart escalating doses of orally self-administered magnesium L-threonate and continue for the remaining 24 weeks of the study.

Prior to magnesium supplementation, blood draws on 3 consecutive days will be used to establish baseline NKG2D expression on CD8+ T cells, numbers of EBV-infected B cells, EBV viral load and intrasubject variability. The number of EBV-infected B cells and other relevant measures will be recorded before and after each supplementation period. The investigator measuring NKG2D expression and the numbers of EBV-infected B cells by FISH (primary outcome measures) will be blinded to the treatment group.

3.2 Study Endpoints

Primary Endpoints

- Cohort 1: Difference between the absolute number of EBV-infected B cells (by EBV FISH) after 12 weeks of oral magnesium supplementation and after 12 weeks of placebo.
- Cohort 2: Difference between NKG2D expression in CD8 T cells after 12 weeks of oral magnesium supplementation and after 12 weeks of placebo.

Secondary Endpoints

- Incidence and severity of AEs throughout the study.
- Contingent upon patient participation in Part II, differences in EBV viral load and number (or percent) of EBV-infected B cells (cohort 1) or NKG2D expression in CD8 T cells (cohort 2) by duration (12 weeks of IV+oral versus 24 weeks of IV+oral) of magnesium supplementation regimen.
- Change in the intracellular pool of free Mg²⁺ by duration of magnesium supplementation regimen.
- Change in NKG2D expression in cohorts 1 and 2.

Exploratory Endpoints

- Change in CD4 T cell counts, B cell counts (or percent), and/or in NKG2D expression on NK (CD3-CD56+) cells.
- Quantification of EBV-infected B cells as determined by flow cytometry and FISH.
- Percent of anemia, neutropenia, thrombocytopenia, and abnormal liver enzymes.
- Difference in number and severity of infections between placebo and magnesium treatment periods.
- Difference in number of health-related days of missed school/work between placebo and magnesium treatment periods.
- Difference in number of emergency room visits and hospital admissions between placebo and magnesium treatment periods.

4 Study Population

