6.3 Part I: Oral study agent (Week 1 to Week 24)

Oral magnesium or placebo (Week 1 to Week 12)

On Day 0, patients will begin to self-administer the oral study agent according to the dose escalation scheme in section 5.4.2.

Dose escalation every 2 weeks (Weeks 2, 4, and 6, or until maximum tolerated dose is reached)

Prior to increasing the study drug dose the study staff will contact patients to review their medication administration, assess for AEs and approve escalation to the next dose. In addition, patients will be contacted 1 week after dose escalation to assess for AEs.

4-week follow-ups (Weeks 4 and 8 +/- 1 week)

Patients will come to NIH for clinical and research evaluations to include:

- Medical history and physical exam

Clinical laboratory evaluations:

- CBC with differential
- Acute care panel, mineral panel, hepatic panel
- EBV by PCR
- CMV by PCR
- CRP
- ESR
- Total and ionized serum magnesium
- TBNK
- Spot urine magnesium

Research assays:

- Intracellular free Mg²⁺
- EBV FISH
- RNA extraction
- NKG2D expression on CD8 T cells and NK cells by flow cytometry
- Storage of serum, plasma, and PBMCs

Week 12 (+/- 1 week)

At the conclusion of 12 weeks of study agent patients will return to NIH for the following evaluations:

- Medical history and physical exam
- EKG

Clinical laboratory evaluations:

- 24-hour urine collection for magnesium
- CBC with differential
- Acute care, mineral and hepatic panels
- Quantitative immunoglobins
- Lymphocyte phenotyping
- CMV by PCR
- EBV by PCR
- ESR
- CRP
- Total and ionized serum magnesium

Research assays:

- Intracellular free Mg²⁺
- EBV FISH
- RNA extraction
- NKG2D expression on CD8 T cells and NK cells by flow cytometry
- Storage of serum, plasma, and PBMCs

Crossover (Week 13-24 +/- 1 week)

To crossover (from magnesium supplementation to placebo or from placebo to magnesium supplementation), patients will return any unused study agent and begin dose escalation with a new oral agent (magnesium or placebo). Patients will be provided dosing instructions and a medication log for recording AEs (Appendix C).

Dose escalation every 2 weeks (2, 4, and 6 weeks after the start of crossover, or until maximum tolerated dose is reached)

Prior to increasing the study drug dose staff will contact patients to review their medication administration, assess for AEs and approve escalation to the next dose. In addition, patients will be contacted 1 week after dose escalation to assess for AEs.

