8.1 Potential Risks

MgSO₄ IV infusion: The AEs associated with parenterally administered magnesium are usually concentration dependent. Magnesium acts peripherally to cause vasodilation. At low doses, it causes flushing and sweating, while at higher doses, it may cause hypermagnesemia and hypotension, depressed reflexes, flaccid paralysis, hypothermia, circulatory collapse, cardiac and central nervous system depression proceeding to respiratory paralysis. The dose (30 mg/kg/day) selected for the current study is intended to prevent serum concentrations >2 mmol/L, a threshold associated with the onset of AEs. Elevations in Alanine Aminotransferase and Aspartate Aminotransferase have been seen with the administration of IV magnesium.

This product contains aluminum that may be toxic. Aluminum may reach toxic levels with prolonged parenteral administration, if kidney function is impaired. Individuals with renal impairment are not eligible to participate in this study.

Magnesium concentration-dependent toxicity, defined as SMCs >2.1 mmol/L (>5 mg/dL) are associated with decreased deep-tendon reflexes, flushing, and somnolence. Serum magnesium concentrations >4.9 mmol/L (>12 mg/dL) are associated with respiratory paralysis and heart block. Magnesium concentrations will be closely monitored in this study.

Oral magnesium L-threonate: Oral magnesium products are typically well tolerated. The most common AEs are diarrhea and nausea, which are typically dose dependent. Dosing in the current study will be based on weight. If dose-limiting AEs occur, patients will be maintained on the highest tolerated dose. Elevations in Alanine Aminotransferase and Aspartate Aminotransferase have been seen with the administration of oral magnesium.

Phlebotomy: may be associated with discomfort, bruising, local hematoma formation and, on rare occasions, infections, lightheadedness, and fainting. The amount of blood drawn for research purposes will be within the limits allowed for adult or pediatric subjects by the NIH CC (Medical Administrative Policy 95-9: Guidelines for Limits of Blood Drawn for Research Purposes in the Clinical Center).

Venous line placement: Venous catheter insertion is associated with bruising, infection, or clot formation. Using proper placement techniques will minimize these risks.

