13.4 Power calculation

Table 3 gives the detectable difference (EBV-infected B cells at end of magnesium – EBV-infected B cells or NKG2D surface expression at end of placebo) with various sample sizes. The differences shown in the table are functions of the standard deviation. For example, with 10 patients if the standard deviation of the differences is 1 there is 90% power to detect a true difference of 1.15. If the standard deviation is 2, there is 90% power to detect a difference of $2.3=1.15*2$. The values in the table are based on using a t-test for the analysis. **Table 3** gives the ratio of the difference to the standard deviation that can be detected with various sample sizes in each group to obtain 90% power. At the end of the study a paired *t*-test will be used to determine whether the difference in the number of EBV-infected B cells or NKG2D expression in CD8+ T cells between the period treated with magnesium and treated with placebo (number of EBV-infected B cells or MFI for NKG2D expression after 3 months of magnesium treatment – number of EBV-infected B cells or MFI for NKG2D expression after 3 months of placebo treatment) is different from 0.

Table 3. Detectable differences with various sample sizes with 90% power and 2-sided type I error rates of 0.05. The differences are shown as functions of the standard deviations

Total sample size (with half of subjects randomized to each sequence)	Difference/standard deviation
10	1.15
12	1.03
14	0.94
16	0.87
18	0.81
20	0.76

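### Reporting blood counts and liver enzymes only as percent abnormal discards much of the precision that a 10- to 20-patient crossover has

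*Combined protocol and SAP*

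**What the plan says.** The endpoint is the third exploratory one in section 3.2, repeated in the Protocol Summary: "Percent of anemia, neutropenia, thrombocytopenia, and abnormal liver enzymes". It serves the objective in section 2.3 concerning "preexisting abnormal biological markers, i.e., NKG2D expression in NK cells, anemia, neutropenia, thrombocytopenia, and abnormal liver enzymes".

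The first exploratory endpoint in the same list keeps its markers on their measured scale: "Change in CD4 T cell counts, B cell counts (or percent), and/or in NKG2D expression on NK (CD3-CD56+) cells".

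The numeric data exist. Sections 6.2 and 6.3 and Appendix B schedule a CBC with differential and a hepatic panel at baseline and at Weeks 4, 8, 12, 16, 20 and 24. Week 12 (listed as "Acute care, mineral and hepatic panels") and Week 24 close the two blinded periods.

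The documents give no cut-off for any of the four conditions, no list of the enzymes that count, and no timepoint, denominator or test. Sections 13.2 to 13.5 do not mention this endpoint.

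**The concern.** The objective asks whether magnesium changes these markers. A percent abnormal answers only through patients who cross a limit. One who improves markedly but stays below it counts as unchanged, as does one who worsens within the normal range.

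The second case matters too, because section 8.1 notes that "Elevations in Alanine Aminotransferase and Aspartate Aminotransferase have been seen with the administration of oral magnesium". A rise in patients already above the limit, or one that stays under it, would not show in a percent.

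In a large trial this loss may be tolerable. Here there are 10 patients per cohort, and each serves as their own control on a numeric scale that the endpoint then sets aside. The documents give no reason for treating these markers differently from the CD4 and B-cell counts.

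**Working it through.** **Inputs from the documents.** n=10 per cohort and 20 in total (Protocol Summary). Detectable difference at 90% power, two-sided 5%: 1.15 SD of the within-patient difference at n=10 and 0.76 SD at n=20 (section 13.4, Table 3).

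**Inputs assumed.** The documents give neither the proportion abnormal on placebo (p) nor the within-patient correlation (ρ). I use p = 30, 50 and 70% and ρ = 0.5, 0.7 and 0.8, with ρ = 0 as an extreme. Values are taken as normal, on the log scale for enzymes.

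**Step 1: reproduce the plan's figure.** Section 13.4 states that "with 10 patients if the standard deviation of the differences is 1 there is 90% power to detect a true difference of 1.15". Paired t-test power comes from the noncentral t with n−1 degrees of freedom and noncentrality d√n. At n=10, d=1.15 it is 0.898; at n=20, d=0.76 it is 0.897. Table 3 reproduces. These effect sizes belong to the primary endpoints and serve here only as a common yardstick.

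**Step 2: what the yes/no scale requires.** In an exact paired (McNemar) comparison only patients who switch status count. Five switches in one direction give p = 2 × 0.5⁵ = 0.0625; six give 2 × 0.5⁶ = 0.031. So at least six patients must switch, all one way if there are only six.

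**Step 3: one case in full (n=10, ρ=0.5, p=30%).** In SDs of a single value the shift is 1.15 × √(2(1−0.5)) = 1.15. The limit lies at Φ⁻¹(0.30) = −0.524. On magnesium, Φ(−0.524 − 1.15) = Φ(−1.674) = 4.7% are abnormal. The bivariate normal gives probability 0.266 of abnormal on placebo and normal on magnesium, and 0.013 of the reverse. Expected switches are 10 × 0.279 = 2.8, against the six needed. Enumerating all outcomes gives power 2.5%.

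**Step 4: the same over the range.** Exact McNemar power at ρ = 0.5 / 0.7 / 0.8, where the paired t-test has 90%:

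| Abnormal on placebo | n=10, shift 1.15 SD | n=20, shift 0.76 SD |
|---|---|---|
| 30% | 2.5 / 1.3 / 0.7% | 20 / 12 / 7% |
| 50% | 14 / 7 / 3% | 39 / 26 / 16% |
| 70% | 24 / 10 / 4% | 43 / 26 / 16% |

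At ρ=0 the highest values are 53% (n=10) and 62% (n=20), with 70 to 80% abnormal. With the less strict mid-p version, the highest values at ρ of 0.5 or more are 44% and 56%. At ρ=0.5, 90% exact power for the 1.15 SD shift would need about 41 patients (p=30%) or 28 (p=50%) instead of 10.

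**Step 5: improvement only in patients who are abnormal.** This is closer to the objective in section 2.3. It was simulated with only truly abnormal patients shifted, ρ = 0.5 to 0.8. For 20 to 30% abnormal, no shift from 0.3 to 8 SD of a single value gave the t-test 90% power. At 8 SD the results were:

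- n=10: t-test 12 to 33%, exact McNemar 0.3 to 3%.
- n=20: t-test 48 to 85%, exact McNemar 5 to 29%.

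At n=20 with 50 to 70% abnormal, where the t-test has about 90%, McNemar gives 31 to 60%.

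**The case against.** The strongest reply is that the comparison uses a test and a target that the plan does not set. The endpoint is exploratory, section 13 plans no test for it, and the 90% power applies only to the two primary endpoints. This stands. A reader might infer that a power claim is broken, or that a real effect would be reported as no effect. Neither follows, because a descriptive percent delivers no such ruling. The figures measure lost information only.

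Second, a uniform shift favours a whole-sample mean, whereas section 2.3 concerns abnormalities already present. This stands in part. Step 5 shows that the mean is diluted when few patients are abnormal, though the yes/no comparison suffers more. It is the reason for adding a summary in patients abnormal at baseline.

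Third, the six-switch minimum is specific to the exact test at one timepoint per period. Mid-p McNemar needs five one-way switches (p = 0.031) and the uncorrected chi-square four (p = 0.046). The endpoint names no timepoint, and these panels are drawn three times per period. So the stronger statement, that no improvement of any size could be shown if fewer than six patients are abnormal, is not general.

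Fourth, whether an anaemia or neutropenia resolved is a fair clinical question. It is, and the percent should stay as description.

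**Conclusion.** The point holds as a cheap gain in precision, not as an error in the plan. Under a uniform shift that a paired t-test would detect with 90% power, the yes/no version has about 1 to 24% exact power at n=10 and 7 to 43% at n=20 (ρ 0.5 to 0.8, 30 to 70% abnormal). The most favourable case examined under that shift is about 62%, at n=20 and zero correlation. All of this rests on assumed prevalence, correlation and normality.

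Two stronger readings go too far. That the endpoint can hardly detect an improvement fits a 10-patient cohort at ρ of 0.5 or more, and 20 patients when about 30% or fewer are abnormal. It does not fit 20 patients with half or more abnormal. Nor is there a fixed minimum gain across all scenarios: at ρ=0 and n=20 the gap is about 28 points (90 − 62), and with improvement confined to abnormal patients it can be 30 (90 − 60). In that setting, with 20 to 30% abnormal, the continuous analysis itself falls short of 90%.

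That five values are involved is an inference: three blood-count conditions, plus ALT and AST, which are named only under risks in section 8.1.

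**What to change.** In section 3.2 and the Protocol Summary, define the endpoint as the within-patient difference, end of magnesium period minus end of placebo period in Part I, in haemoglobin, absolute neutrophil count, platelet count, and log ALT and log AST. In section 13, state that each is reported as a mean paired difference with 95% confidence interval, as section 13.3 does for the primary endpoints, with a supporting summary restricted to patients abnormal at baseline to match section 2.3. Keep the percent abnormal in each period as description, and state the cut-offs and denominator it uses.

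The cost is a few lines of text and five short paired analyses of values already collected, with no new visits, samples or patients. The drawback is that a mean change is less directly clinical than normalisation, which the retained percent covers.
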